2.11 Unscheduled Visits

An unscheduled visit may be performed at any time during the study at the subject's request or as deemed necessary by the site Investigator. The date and reason for the unscheduled visit will be recorded in the source documentation.

2.12 Replacement of Subjects

Replacement of subjects who have withdrawn or been withdrawn from the study will be allowed to be replaced with prior approval from the sponsor and/or IRB

2.13 Schedule of Visits and Procedures

	Visit #1*	Visit #2-6	Visit #7	Visit #8	Visit #9
Procedure	Screening and Pre-treatment Procedures	Treatment Visit(s) 1-5 (3-14 days Apart)	Follow up and Biopsy 0, 1, 3, 7, 24, 21 or 30 days Post Last Tx (Optional)	Follow Up 1 Month Post Last Tx (+/- 1 Week) (Optional)	Follow Up 3 Months Post Last Tx (+/- 1 Week) (Optional)
Medical History	X				
Pregnancy Verification	X	X			
Informed Consent	X				
Treatment		X			
Parameters		X	X		
Treatment Discomfort/ Pain Evaluation		X			
Subject Treatment Experience Questionnaire		X			
Clinician Treatment Questionnaire		X			
Biopsies			X		
Photographs (Vivosight)	X		X	X	X
Photographs (2D, 3D)	X		X	X	X
Subject Follow Up Questionnaire				X	X
Subject Satisfaction Questionnaire				X	X
Clinician Satisfaction Questionnaire				X	X
Adverse Event Assessment	X	X	X	X	X

*Screening and Pre-treatment Procedures may occur at the same time as the Treatment Visit #1.

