2.0 PROTOCOL

2.1 Protocol Methodology and Analysis

Methodology:

Subjects are to be enrolled in this clinical study if they are a healthy male or female 18 – 65 years of age. Up to 50 subjects will be enrolled at 2 study centers. Subjects will attend a screening/pretreatment visit which may be performed on the same day as the treatment visit. Subjects may receive up to 5 treatments with the study device. Subjects may also receive treatment

with a similar shockwave device. Subjects may be consented to have biopsies collected at a specific time after their final treatment, which will occur up to 30 days post treatment. Follow up visits may occur 30 and 90 days post last treatment visit. An unscheduled visit or phone call may be performed at any time during the study at the request of the subject or as deemed necessary by the site Investigator.

Analysis:

Upcoming generations are proving to have an interest in non-ablative aesthetic treatments and will drive demand for innovated products, procedures, and practice design.¹ Due to this shift in patient base, practices need to evolve to adapt to the newer generational ideologies. This device will be using the SoftWave device to collect additional data and imaging. Although this device is cleared for use by the U.S. Food and Drug Administration, there is a need to collect additional data, images, and tissue response to expand marketing claims.

Relevance:

There is an increasing demand for new methods and additional cleared indications for non-invasive treatments using shockwave therapy. Another device currently on the market cleared for use is, but are not limited to, the dermaPACE® System.

Testability:

The SoftWave device, had been previously cleared for the activation of connective tissue (FDA 510(k) K182682), the treatment of chronic, full thickness diabetic foot ulcers (FDA 510(k) K191961), and the treatment of superficial partial thickness second degree burns in adults (FDA 510(k) K200926). This study will utilize the collection of data and imaging to support additional marketing claims.

Compatibility:

Although shock wave technology is a well-known and widely use technique for non-invasive treatments, there is still a need to collect additional data and images, and expand marketing claims and device use.

Predictive power:

Assuming there is an acceptable side effect profile, it would be appropriate to expect results for other marketable indications.

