2.5 Informed Consent Process and Enrollment

Subjects will be asked to review the post treatment instructions prior to signing the informed consent form and their involvement in the study. They must also review the site's COVID-19 procedures and agree to follow protocols put in place at the site relating to COVID-19. Subjects who sign the informed consent will be screened to confirm eligibility and, if eligible, will be assigned a subject identification number. Subjects will be de-identified through their subject identification number, which will be stored in a secure location. Subject identification numbers will be generated chronologically and assigned only to subjects who have met all the study selection criteria and have signed the informed consent form. The informed consent will be obtained prior to a subject's involvement in any study related procedures. A subject will be considered enrolled in the study once they have signed the informed consent form.

The following post treatment instructions will be reviewed with subject:

- You can return to a normal lifestyle immediately after treatment including light athletic workouts but avoid extreme exercise or activities that may reinjure the damaged area through overuse. The inflammation may have eliminated pain but it takes time to heal.
- You can continue previously prescribed therapies, such as stretching.
- Avoid ice and anti-inflammatory medicine (i.e. NSAIDs, such as Ibuprofen) for several days after therapy as this may reduce outcomes.
- Drink lots of water.
- You may feel tired after a SoftWave treatment.
- You may experience a tingling sensation in the treatment area for several days after therapy. This is good.
- You may experience mild soreness or stiffness during the next 48 hours. This is normal.

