2.9 Follow Up

- Subjects will return for follow up visits at 30 and 90 days post last treatment.
- Photographs will be taken and adverse events will be documented and each follow up visit.
- Clinician and subject questionnaires may be performed at each follow up visits.
- Any subject affected by COVID-19 that is not able to attend their follow up visits to complete the study will be asked to return to the site for a final follow up visit within 1 year of last treatment.
- Some subjects may have an incomplete response or no response by the end of the study. At the end of the study, treatments using an FDA approved/cleared treatment method may be discussed with the subject and obtained at the cost of the subject.

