2.15 Statistical Analysis**2.15.1 Hypothesis**

For this study to be considered a success, the average pain score is acceptable to the Physician as it relates to the type of treatment.

For additional objectives to be considered a success, the following criteria must be met:

- The side effect profile (adverse events) is acceptable to the Physician as it relates to the type of treatment.
- The subject satisfaction rates at the follow up visit will be $\geq 80\%$ (optional).
- Correct identification of pre-treatment images when compared to post treatment (30 and/or 90 day) images will be $\geq 80\%$ (optional).
- Successful collection of biopsies (optional).
- Successful collection of treatment assessment questionnaires (optional).

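### Section 2.9 says subjects return at 30 and 90 days, but section 2.1 and the schedule leave those visits optional, so no adverse event inquiry after the last treatment is assured

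*Combined protocol and SAP*

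**What the plan says.** Three places in the current text describe the same visits differently.

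- Section 2.9 states them as part of every subject's course: "Subjects will return for follow up visits at 30 and 90 days post last treatment". It ties safety data to them: "Photographs will be taken and adverse events will be documented and each follow up visit".
- Section 2.1 is permissive: "Follow up visits may occur 30 and 90 days post last treatment visit".
- The schedule in section 2.13 labels Visit 8 "Follow Up 1 Month Post Last Tx (+/- 1 Week) (Optional" and Visit 9 "Follow Up 3 Months Post Last Tx (+/- 1 Week) (Optional". Visit 7, the biopsy and follow-up visit, ends its label the same way: "30 days Post Last Tx (Optional".

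Nothing says which text governs. The schedule places adverse event assessment at every visit, and places the satisfaction questionnaires only at Visits 8 and 9.

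Section 2.5 tells subjects what may follow treatment: soreness or stiffness over the next 48 hours, and "You may experience a tingling sensation in the treatment area for several days after therapy". In section 1.2 the collection of adverse events is a safety objective with no optional label. Section 2.15.1 lists, also without that label, the criterion "The side effect profile (adverse events) is acceptable to the Physician as it relates to the type of treatment". The two criteria of at least 80%, for satisfaction and for identifying pre-treatment images, are labelled optional and have no stated denominator. Section 2.15.3 leaves the missing-data method to be chosen later.

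**The concern.** Under the schedule, every visit after the last treatment visit is optional. A subject treated once, or any subject after the final treatment, can complete the study with no planned question about adverse events after leaving the clinic. The side-effect profile put to the physician would then pool subjects asked weeks or months later with subjects last asked on the treatment day. Effects that appear in between would tend to be under-counted, and the report would not show by how much.

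The satisfaction and photograph results, if reported, would rest only on those who attended. If attendance is related to outcome, the rate among attendees differs from the rate in the treated group. This matters because the stated purpose of the data is to support marketing claims.

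There is also a conduct problem. A missed 30-day visit departs from section 2.9 but not from the schedule, so two centers could apply the deviation rules and the per-protocol set of section 2.15.3 differently.

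**Working it through.** **Step 1. Which scheduled adverse event assessments are assured?** (sections 2.7 and 2.13)

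- Treatment visits: not labelled optional, 3 to 14 days apart, up to five. For a subject with two or more treatments, each later treatment visit follows up the one before it. Soreness over 48 hours is covered, and tingling of several days largely so.
- After the last treatment: Visits 7, 8 and 9 only, all optional. None is assured.
- A subject treated once, with screening on the same day as the schedule allows, has no assured assessment after that day.

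Planned observation after the last treatment can therefore be 0 days. On the ordinary schedule it can reach 90 + 7 = 97 days, taking three months as 90 days. Section 2.9 also allows a final visit within 1 year for subjects affected by COVID-19, so 97 days is not the maximum.

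**Step 2. What could incomplete attendance do?** The only design figure is 50 subjects (section 2.15.2). It comes with no error rate, power, effect size or dropout rate, so it cannot be reproduced, and this point does not dispute it. The attendance n, the 5% incidence and the 80% satisfaction among attendees are assumptions chosen to show a range.

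- Chance that at least one of n subjects asked has a delayed event of 5% incidence: 1 − 0.95^n
- One-sided 95% upper limit after zero events in n: 1 − 0.05^(1/n)
- Satisfaction over all 50, if 0.8n attendees are satisfied: from 0.8n/50 (no non-attender satisfied) to (0.8n + 50 − n)/50 (all satisfied)

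| Attend (n of 50) | At least one event | Upper limit after zero | Satisfaction over all 50 |
|---|---|---|---|
| 50 | 92.3% | 5.8% | 40/50 = 80% |
| 40 | 87.1% | 7.2% | 32/50 to 42/50 = 64% to 84% |
| 30 | 78.5% | 9.5% | 24/50 to 44/50 = 48% to 88% |
| 25 | 72.3% | 11.3% | 20/50 to 45/50 = 40% to 90% |

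**Step 3. Could selective attendance reverse the 80% criterion?** Suppose 70% are truly satisfied, and 90% of satisfied but 45% of unsatisfied subjects attend (all assumed). The observed rate is 0.70 × 0.90 / (0.70 × 0.90 + 0.30 × 0.45) = 0.63/0.765 = 82.4%, a pass. With equal attendance it is 70%, a fail.

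**Step 4. Would dividing by all treated repair it?** Suppose 30 attend and 27 are satisfied, and 10 of the 20 non-attenders are in fact satisfied (assumed). Among attendees the rate is 27/30 = 90%. The true rate is (27 + 10)/50 = 74%. Satisfied over all treated is 27/50 = 54%. That figure is 20 points below the truth, while the attendee rate is 16 points above it. Satisfied over all treated is a lower bound, not an estimate.

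**The case against.** The best defence is that safety capture does not depend on these visits alone. Section 14.0 tells subjects they may contact the investigator at any time and has adverse events captured throughout the study. Sections 2.1 and 2.11 allow unscheduled visits, and section 2.1 calls as well. Section 12.0 asks withdrawing subjects to complete a final visit. Section 2.3 requires subjects to accept an obligation to attend all visits. This stands in part and softens the gap. It does not close it, because no one is required to ask a subject who simply finishes under the schedule. Section 2.5 also tells subjects that tingling is good and soreness normal, which makes spontaneous reports less likely.

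Four stronger readings are tempting, and the documents do not support them.

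- A reader might infer that every visit able to detect post-treatment effects is optional. Treatment visits are not, and they cover effects of earlier treatments.
- A reader might infer that subjects select themselves into follow-up. No section says whether subject, site or sponsor exercises the option. The and/or wording for 30 and 90 days in sections 1.2 and 2.15.1 also fits a choice made for the whole study, in which case there need be no selection among subjects.
- A reader might count hematoma and hypoesthesia as expected delayed effects. Section 2.14 lists them without any onset after the clinic visit; only tingling and soreness have such timing, in section 2.5.
- A reader might take the ordinary schedule as the limit of observation. The one-year COVID-19 provision contradicts that.

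It is also fair to say that the satisfaction and photograph criteria are optional, and that the adverse event criterion has no numerical threshold to be missed.

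**Conclusion.** The point holds. Sections 2.1, 2.9 and 2.13 conflict in current text. Under the schedule, a treated subject can finish with no planned adverse event inquiry after the last treatment, while the adverse event objective and criterion are not optional. The gap is confined to the period after the last treatment, which is the whole post-treatment period for a subject treated once.

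If the optional 80% criteria are reported, they would describe attendees only, with no stated denominator. How far this could mislead depends on attendance, which the documents do not give. The figures above are illustrations, not predictions, and they assume that every attender is asked and recalls accurately. The primary objective, pain during treatment, is unaffected. The wording should be corrected, but the conflict does not undermine the main result.

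**What to change.** 1. Reconcile sections 2.1, 2.9 and 2.13 on whether Visits 8 and 9 are required. If they are optional, say who decides and whether the choice is made per subject or for the study.
2. Reconcile the photograph wording in the same revision. Section 1.2 makes photographic evaluation optional, section 2.9 has photographs taken at each follow-up visit, Evaluation Methods has them at all visits, and section 13.0 bars anyone who declines them. Letting section 2.9 govern while calling imaging optional would leave a contradiction.
3. If the visits stay optional, add one scheduled adverse event inquiry of every treated subject after the last treatment. A telephone call, which section 2.1 already allows, is enough. The sponsor should set its timing with recall in mind, since the effects described in section 2.5 last from 48 hours to several days.
4. Report adverse events with the number of subjects assessed and their days of observation.
5. Report satisfaction and photograph identification with the number assessed out of all treated and the rate among those assessed. Add satisfied over all treated, labelled as a worst-case bound.

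The cost is protocol wording and at most one call per non-attender. The worst-case satisfaction figure may look clearly less favourable: 54% against 90% in the illustration.

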2.13 Evaluation Methods

Photographs:

Photographs will be taken at all visits and will be used to assess efficacy and safety of treatment.

Treatment Discomfort/Pain Evaluation:

Subjects will be asked to report the general level of treatment discomfort on a scale of 0 (none) to 10 (maximum intolerable pain) using the universal pain assessment tool (Appendix B)

Subject and Clinician Satisfaction Questionnaire:

The subject will be asked their level of satisfaction using a 6-point Likert scale that ranges from “extremely satisfied” to “extremely unsatisfied.”

Subject Satisfaction	
Rating	Description
6	Extremely Satisfied
5	Satisfied
4	Slightly Satisfied
3	Slightly Unsatisfied
2	Dissatisfied
1	Extremely Unsatisfied

Blinded Evaluation:

Three blinded independent reviewers will perform a photographic evaluation in which they will be asked to identify pre-treatment images when compared to post treatment images. The reviewers will be Board Certified Dermatologist and/or Surgeons and be chosen based on availability and have relevant clinical experience. They will attend a training session prior to grading.

2.14 Adverse Event Recording

All data captured must be supported by the Investigator's timely assessment and documentation of the adverse event in the case report forms or source documents. All documented adverse events will be reviewed by the Sponsor or designee to determine whether the adverse event meets regulatory reporting requirements and to ensure timely adverse event reporting to meet local and global regulatory requirements. All adverse events must be followed until their resolution.

Adverse Events Pertaining to the SoftWave Device:

Potential adverse effects associated with shock wave treatments include those listed below:

- Transient moderate increase in pain
- Redness and swelling
- Hematoma and petechial hemorrhage
- Headaches and fainting during extracorporeal shock wave treatments
- Short-term hypoesthesia
- Nausea during therapy
- Tingling during therapy

Adverse Events Pertaining to the Marker:

Using a marker has minimal risks and may produce effects on the body such as redness or a rash.

Adverse Events Pertaining to Ultrasound Gel:

The gel is a water-based gel that may be placed on the skin during treatment. No known adverse events are documented. However, an allergic reaction is always possible when placing a topical gel onto the skin. Allergic reaction may include a mild reaction such as skin redness, irritation, or hives.

Biopsies

Complication with biopsies can include pain, redness, swelling, infection, bleeding, scarring and skin texture irregularities.

Lidocaine

You may experience pain and numbness at the site of the injection. You may also experience redness, rash, infection, skin damage or nerve damage at the site of the injection. You may experience temporary loss of sensation and muscle function at the site of injection.

1% lidocaine (Lidocaine) with Epinephrine Injection

Lidocaine with epinephrine contains the preservative sodium metabisulfite which may cause allergic-type reactions including anaphylactic symptoms such as itching, hives, swollen areas of the body, and/or trouble breathing and life-threatening or less severe asthmatic episodes in certain susceptible people.

Other Cautions:

Incomplete response or no response may occur since some subjects may not respond to treatment.

2.15 Statistical Analysis**2.15.1 Hypothesis**

For this study to be considered a success, the average pain score is acceptable to the Physician as it relates to the type of treatment.

For additional objectives to be considered a success, the following criteria must be met:

- The side effect profile (adverse events) is acceptable to the Physician as it relates to the type of treatment.
- The subject satisfaction rates at the follow up visit will be $\geq 80\%$ (optional).
- Correct identification of pre-treatment images when compared to post treatment (30 and/or 90 day) images will be $\geq 80\%$ (optional).
- Successful collection of biopsies (optional).
- Successful collection of treatment assessment questionnaires (optional).

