1.2 Objectives

1. Primary Objective:
 - Collection of Treatment Discomfort/Pain Evaluation
2. Additional Objectives:
 - Evaluation of tissue response through Biopsies at multiple timepoints up to 30 days post treatment (optional):
 - Sample staining as appropriate, such as H&E
 - Nano-string for Gene Expression
 - Device comparison treatment with similar low-intensity shockwave device (optional).
 - Photographic evaluation with Vivosight imaging at the 30 and/or 90 day follow up compared to baseline (optional).
 - Photographic evaluation with 2D and/or 3D imaging at the 30 and/or 90 day follow up compared to baseline (optional).
 - Subject treatment assessment through questionnaires (optional):
 - Subject treatment experience questionnaire
 - Subject follow up questionnaire
 - Subject satisfaction questionnaire
 - Clinician treatment assessment through questionnaires (optional):
 - Clinician treatment questionnaire
 - Clinician satisfaction questionnaire
3. Safety Objectives:
 - Collection of Adverse Events

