2.15.3 Patient Populations

Interim results may be collected and reported. All data will be analyzed at the end of the study on a per device basis as well as overall. The primary analysis will be performed by the intention-to-treat approach. Everyone who begins the treatment is part of the study whether he or she completes the study or not. Additional per-protocol analysis may also be performed on subjects who complete the entire clinical trial according to the protocol. The most appropriate method of handling missing values will be chosen based on the individual trial goals, endpoints and context.

The analysis of demographic, medical history, and efficacy variables will be based on all patients who are randomized and receive at least one treatment. The analysis of safety data will be based on all patients who are randomized, receive at least one treatment, and have at least some safety data.

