2.15.6 Analysis of Safety Variables

Safety will be assessed through the degree of pain/discomfort related to the procedure (universal pain scale) and the collection of Adverse Events throughout the course of the study. For each treatment group these variables will be summarized. The summaries will include the number and percent of patients for each outcome. No statistical comparisons will be performed for any of these variables.

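### Study success rests on the Physician finding an average pain score acceptable, with no level, judge, time or deciding average fixed in advance

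*Combined protocol and SAP*

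**What the plan says.** Section 1.2 gives one primary objective: "Collection of Treatment Discomfort/Pain Evaluation". Section 2.15.1, under the title Hypothesis, turns this into a verdict. The study succeeds if "the average pain score is acceptable to the Physician as it relates to the type of treatment". The first criterion for the additional objectives, the adverse-event profile, is also left to the Physician's acceptance and is not marked optional. Two optional criteria in the same list do carry a number. One begins "The subject satisfaction rates at the follow up visit will be" and sets at least 80%; the other sets at least 80% for correct identification of pre-treatment images.

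Section 2.15.6 handles pain as a safety variable, summarised for each treatment group. "The summaries will include the number and percent of patients for each outcome", and "No statistical comparisons will be performed for any of these variables". Section 2.15.3 adds "All data will be analyzed at the end of the study on a per device basis as well as overall", allows early viewing ("Interim results may be collected and reported"), and leaves missing data open: "The most appropriate method of handling missing values will be chosen based on the individual trial goals, endpoints and context".

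The design is open label (2.2), with up to 50 subjects at two centers and possible treatment with a second device (2.1). A subject may have up to five treatments (2.7), and the visit schedule places the pain evaluation at the treatment visits.

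**The concern.** A success criterion is informative only if some results would fail it and those results are named before the data are seen. Here the criterion is a judgement by an unnamed person, at an unstated time, against an unstated standard, of an average that could be built in several ways. The people who judge may already know the data: treatment is open label, interim results may be reported, and section 5.0 lets the sponsor request data after each visit.

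This is the study's only overall success criterion, and sections 1.1 and 2.1 say that the study is meant to support additional marketing claims. What is at stake is the reported verdict. The pain scores themselves remain usable as a description.

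**Working it through.** **1. The plan's own figure.** Section 2.15.2 sets 50 subjects including departures, based on the need for data. It gives no limit, standard deviation, power, precision target or dropout rate, so the 50 cannot be reproduced or refuted, and it cannot be tied to the success criterion.

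**2. What a decision rule needs, against what the text gives.**

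| Element | Nearest text | Given? |
|---|---|---|
| Scale | 0 to 10, subject-reported (2.7, Evaluation Methods, Appendix B) | Yes |
| Population | All who begin treatment (2.15.3) | Yes |
| Acceptable level | 2.15.1 | No |
| Who decides | The Physician (2.15.1); two centers (2.1) | Not identified |
| When | Nothing in 2.15.1; interim reporting allowed (2.15.3) | No |
| Which sessions | Up to five treatments (2.7) | No |
| Which device mean | Per device and overall (2.15.3) | Both planned; the deciding one not named |
| Summary of pain | An average (2.15.1); number and percent (2.15.6) | Mean not in the 2.15.6 list |

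No value between 0 and 10 is classified in advance as success or failure. The probability of declaring success at a given true mean is therefore not a function of anything in the plan, and no type I error can be computed.

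**3. How far the average depends on its construction (illustration only; all inputs invented).** Suppose 10 of 50 subjects score 7 at every session and 40 score 4.
- Mean of subject means: (10×7 + 40×4)/50 = 230/50 = 4.60.
- Pooled over sessions, if the 10 have one session and the 40 have five: (10×1×7 + 40×5×4)/(10 + 200) = 870/210 = 4.14, which is 0.46 lower.
- Pooled, with the session counts reversed: (10×5×7 + 40×1×4)/(50 + 40) = 510/90 = 5.67, which is 1.07 higher.

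The shift can go either way, so no direction of bias is established.

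For devices, let w be the share of scores from the comparison device and D the comparison mean minus the SoftWave mean. The overall mean minus the SoftWave mean is w×D. With w assumed at 20% to 50%, that is 0.2 to 0.5 points for each point of D.

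**4. Precision of a descriptive mean (assumed SD 1.5 to 3, one value per subject).** The 95% CI half-width is t(0.975, N−1)×SD/√N.
- N = 50: 2.010×1.5/7.071 = 0.43 and 2.010×3/7.071 = 0.85.
- N = 40: 2.023×1.5/6.325 = 0.48 and 2.023×3/6.325 = 0.96.

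Enrollment is up to 50 including departures, so N = 50 is the best case. A descriptive mean with its interval is feasible at this size.

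**The case against.** The strongest reply is that this is a data-collection study. The primary objective is only to collect pain scores, no statistical comparison is planned, no passage states a pain marketing claim, and clinical judgement of tolerability is legitimate. All of that stands, and it is the reason for preferring a descriptive endpoint. It does not rescue the success sentence, which adds a verdict that the planned analysis does not support.

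The plan also covers more than a quick reading suggests. Section 2.15.3 already fixes the population and a per-device analysis, and 2.15.6 already summarises pain by treatment group, so a SoftWave-only summary is planned. Section 2.15.1 does name an average, and the list in 2.15.6 does not exclude one. What remains is that the deciding average is not named and that a mean is missing from the list.

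The type of treatment may simply mean shock wave treatment, and the Protocol Manual and Instructions for Use, listed as attachments, were not supplied. The point therefore does not rest on undefined treatment types. Nor does it rest on the section numbering, which passes from 2.15.4 to 2.15.6.

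A reader might infer that no result could ever count as failure, or that the standard will in fact be set after the data are seen. The documents support neither. The Physician could find an average unacceptable, and the provisions for interim results and visit-by-visit data permit early viewing without showing how it would be used.

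**Conclusion.** The concern holds in this form: failure is not defined in advance, and neither the person who decides, the time of judgement nor the deciding average is fixed. Followed exactly, the plan can yield a statement of success that carries no evidential weight. The adverse-event criterion shares the defect. This should be corrected before any result is reported, because a standard written after open-label pain data have been reviewed cannot repair it.

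The size of the error cannot be stated as a probability. The shifts of 0.46 and 1.07 points, and of 0.2 to 0.5 per point of device difference, show only that the undefined choices can move the average; they are not estimates for this study. The conclusion rests on the supplied text and would change only if a document outside it fixed the missing elements before data review. It does not imply that 50 subjects are too few or that the pain data are unusable.

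**What to change.** 1. In 2.15.1, delete both statements that make success depend on the Physician's acceptance. Label pain, the primary objective, and adverse events as descriptive. This agrees with 1.2 and with the absence of comparisons in 2.15.6.
2. In 2.15.6, add N, mean, SD and 95% CI of pain for SoftWave beside the counts and percents. Use one prespecified value per subject, for example the subject's own mean across SoftWave sessions, among all who begin treatment. Report the comparison device separately and state the number of missing scores.
3. If the sponsor wants to keep a success claim, it must write its own numeric limit and decision rule into the protocol before any pain data are reviewed, naming the deciding average, and reconcile this with 2.15.6. If pain data have already been reviewed, only the descriptive route remains.

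The cost is wording and a minor analysis of scores already collected, with no extra subjects or visits. The real price is that the study gives up a pain success claim or, under item 3, can miss it.
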